6.2. Derived Variables

Refer to Table 12 below for derived variables and their definitions for various study parameters.

Table 12: Derived Variables and Definition

Variable	Definition
Height (cm)	If height is recorded in inches, then height is equal to the recorded value multiplied by 2.54 and then rounded to 1 decimal place.
Weight (kg)	If weight is recorded in pounds, then weight is equal to the recorded value multiplied by 0.454 and then rounded to 1 decimal place.
Baseline	Baseline is defined as the last non-missing measurement/assessment prior to the CCH injections given at Day 1. Any assessments performed at an unscheduled visit will be considered in the calculation of baseline, if the unscheduled assessment is the closest value preceding the study drug injection.
Study Day	Study Day will be computed as Date of Assessment – Date of Day 1 + 1 for assessments on or after Day 1, else study day will be computed as Date of Assessment – Date of Day 1.
Change from Baseline	Change from baseline will be derived as post-baseline visit/time point value – the baseline value.
Last Date in the Study	Last date in study is defined as: 
 • The date of Day 265 (Biopsy follow-up visit) if the subject completes the study • The date of early termination visit if the subject is terminated early from study at a non-scheduled visit • The date of the latest scheduled visit if the subject is terminated early from study at a scheduled visit or lost to follow-up.
Age (Years) at EFP Symptom Onset	Date of EFP symptoms reported – Date of Birth/365.25. See Section 6.3.1.3 for handling of partial or unknown EFP symptom onset dates.
Time (Years) Since Last EFP Treatment	Date of most recent EFP treatment – Date of informed consent/365.25. See Section 6.3.1.3 for handling of partial or unknown EFP treatment dates.
Duration (Minutes) of Exposure at Each Visit	Date/Time of Last Injection – Date/Time of First Injection
Duration of AE(Days)	AE end date – AE start date + 1
AE Onset Day	AE start date – Date of Day 1 + 1.

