^a Performed prior to any study-required assessments, unless exceptions granted for standard of care procedures. A separate informed consent may be used for HIV testing and must be signed before the sample is collected, if required.

^b Should be reassessed and verified prior to dosing.

^c Vital signs will be collected up to 4 hours prior to, and at 15 and 30 minutes after, study treatment administration on Days 1, 22, and 43.

^d Urine pregnancy test should be completed prior to the MRI.

^e At screening all 4 potential treatment areas (each buttock and each thigh) will be imaged; and CR-PCSS, PR-PCSS, and Hexsel CSS assessments will be done for each potential treatment area (each buttock and each thigh).

^f Before and after marking dimples for treatment. No manipulation of the treatment area should be done prior to the “before” photographs.

^g Screening MRIs will be performed after all other screening assessments (except the biopsy) have been completed. MRIs may be repeated within the screening window as often as necessary to obtain evaluable images.

^h The Day 71 and Day 251 MRIs may be performed up to 7 days prior to the indicated visit. The MRI must be completed before the biopsy required for these visits. The Day 251/Early Termination MRI is not required for subjects who withdraw from the study (early termination). The Day 71 and Day 251 MRIs may be repeated as often as necessary to obtain an evaluable image.

Table 1: Schedule of Activities (Continued)

ⁱ The screening biopsy will be performed after all other screening assessments (including MRI) are completed. The screening biopsy will be performed at least 14 days prior to the Day 1 Treatment Visit. The investigator must examine and confirm sufficient healing of the biopsy site before dosing on Day 1. The timing of all subsequent visits will be based on the actual date that the first dose of CCH is administered.

^j The Day 71 and Day 251 imaging for efficacy, PR-PCSS, and CR-PCSS must be completed prior to the biopsy sample collection required at those visits. The Day 251/Early Termination biopsy is not required for subjects who withdraw from the study (early termination). For subjects who received less than 3 doses of CCH prior to 18 March 2020, no Day 71 or Day 251 biopsy samples will be collected.

^k Visit not required for subjects who had less than 3 doses of CCH prior to 18 March 2020.

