^l Adverse events (AE)/serious adverse events (SAE) will be captured from time of informed consent signature until the Day 265 Visit or until 28 days after last dose of study drug whichever is later. There is no time limit on collection of SAEs considered to be related to study treatment.

Note: Unless otherwise stated above or outlined below (and with the exception of injection site reactions/local tolerability in the areas treated), all assessments should be completed prior to dosing on treatment days (Days 1, 22, and 43).

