8.2.5. Vital Signs

Vital signs will be obtained at times outlined in the Schedule of Events and after the subject has been seated for 5 minutes (minimum) and will include systolic and diastolic blood pressures, pulse rate, respiratory rate, and body temperature. The results, date, and time for all vital sign assessments will be recorded.

On study treatment days (Days 1, 22, and 43), vital signs will be taken up to 4 hours prior to dosing and at 15 minutes and 30 minutes after dosing (body temperature is not required at the 15 minute postdose time point). The subject's vital signs must be stable, or repeated until stable before the subject can leave direct observation.

The investigator will review all vital sign values for clinical significance. Any vital sign value meeting the investigator's or sponsor's criteria for clinical significance will be recorded as an AE (or SAE, if appropriate).

8.2.6. *Electrocardiogram*

A 12-lead ECG recording will be conducted at the Screening Visit. The subject should be in a supine position for at least 5 minutes before the recording is conducted. Lead position will be that of a standard 12-lead ECG; no additional or special lead placements will be necessary. The ECG record should include a minimum of 5 heart cycles (beats).

If the ECG report shows QT prolongation with QTc \geq 450 ms, the investigator should repeat the ECG within 1 hour. If the initial findings are confirmed, the investigator should exclude the subject from study participation.

The investigator will review all other ECG results for clinical significance. Any ECG result meeting the investigator's criteria for clinical significance will be recorded as an AE (or SAE, if appropriate).

8.2.7. *Clinical Laboratory Determinations (Hematology, Chemistry, and Urinalysis)*

Clinical laboratory tests will be conducted according to the Schedule of Activities (Section 1.2). Required clinical laboratory tests are outlined in Section 10.2. Clinical laboratory tests will be performed by a designated central laboratory. The site will be provided with instructions for specimen collection, preparation, packaging and transport. The results of the tests will be returned to the investigational site.

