4.6.3. Potentially Clinically Important Vital Sign Values

Vital sign values are PCI if they meet either or both of the observed value criteria and the change from baseline criteria. The PCI vital sign values are presented in [Table 10](#) below.

Table 10: Potentially Clinically Important Vital Sign Criteria

Parameter	PCI Low	PCI High
Systolic Blood Pressure	≤ 90 mmHg and/or decrease ≥ 20 mmHg from baseline	≥ 180 mmHg and/or increase ≥ 20 mmHg from baseline
Diastolic Blood Pressure	≤ 50 mmHg and/or decrease ≥ 15 mmHg from baseline	≥ 105 mmHg and/or increase ≥ 15 mmHg from baseline
Pulse Rate	≤ 50 bpm and/or decrease ≥ 15 bpm from baseline	≥ 120 bpm and/or increase ≥ 15 bpm from baseline
Respiratory Rate	≤ 8 brpm and/or decrease ≥ 7 brpm from baseline	≥ 25 brpm and/or increase ≥ 7 brpm from baseline
Temperature		$\geq 38.3^{\circ}\text{C}$ and/or increase $\geq 1.1^{\circ}\text{C}$ from baseline

bpm=Beats per minute; brpm=Breaths per minute

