7.7.4. Vital Signs and Body Weight

Vital signs parameters (blood pressure, pulse rate, respiratory rate, and body temperature) and body weight will be summarized by treatment region, not treated and overall using descriptive statistics for observed and change from baseline values for all visits/time points.

PCI vital sign values will be summarized by frequency counts and percentages. Refer to [Table 10](#) for PCI criteria.

Individual vital sign measurements including pulse rate, systolic blood pressure, diastolic blood pressure, respiratory rate, and body temperature will be listed.

7.7.5. 12-Lead ECG

A subject listing will be presented for the investigator interpretation.

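### Post-injection vital signs on Days 22 and 43 are compared with the pre-Day 1 value, although a same-day pre-dose value is collected; a session baseline would correct the change and PCI tables at no data cost

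*SAP*

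**What the plan says.** Protocol 8.2.5 sets the timing on each dosing day: "vital signs will be taken up to 4 hours prior to dosing and at 15 minutes and 30 minutes after dosing". The footnote to the Schedule of Activities (Protocol 1.2) agrees. So each of the three sessions has its own pre-dose reading and two post-dose readings.

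The SAP has a single reference. Table 12 in SAP 6.2 states: "Baseline is defined as the last non-missing measurement/assessment prior to the CCH injections given at Day 1". The same table derives change by subtracting that baseline: "Change from baseline will be derived as post-baseline visit/time point value" is the first term. SAP 7.7.4 summarises vital signs "using descriptive statistics for observed and change from baseline values for all visits/time points". SAP 4.6.3 states: "Vital sign values are PCI if they meet either or both of the observed value criteria and the change from baseline criteria". One change limit in Table 10 is, for systolic pressure, "increase ≥ 20 mmHg from baseline"; the limit for a fall has the same size. Diastolic pressure and pulse have limits of 15 mmHg and 15 bpm in either direction.

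Neither document defines a baseline for each session or plans a change from the same-day pre-dose value on Day 22 or Day 43.

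**The concern.** The readings before dosing and at 15 and 30 minutes form a short before-and-after design. Protocol 6.3 describes CCH as a foreign protein and requires 30 minutes of direct observation for immediate immunological events. Sessions II and III are the re-exposures, so the quantity of interest there is the change within the session.

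The SAP calculates something else. At four of the six post-dose time points (two sessions, two readings each), the tabulated change is the acute change plus whatever shift has occurred since Day 1. Because a change alone is enough for a PCI flag, that shift can trigger a flag or cancel a real acute change. With 12 new subjects (Protocol 4.1), a few spurious flags could alter how the table is read.

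**Working it through.** **Interval.** Day 22 − Day 1 = 21 days (18–24 with the ±3-day window). Day 43 − Day 1 = 42 days (39–45). It is longer for anyone resuming doses after the March 2020 suspension. Protocol 2.1 reports 7 subjects dosed, of whom 2 had all three doses, so 7 − 2 = 5 could fall in this group.

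**Both errors are possible (illustrative systolic values, mmHg).**
- Hidden: Day 1 130; Day 22 pre-dose 112, post-dose 134. Against Day 1: 134 − 130 = +4, no flag. Same day: 134 − 112 = +22, flag.
- Spurious: Day 1 106; Day 22 pre-dose 125, post-dose 127. Against Day 1: 127 − 106 = +21, flag. Same day: 127 − 125 = +2, no flag.

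**How often.** The plan states no error rate, so there is no figure to reproduce. The documents give no vital-sign SDs; those below are assumptions.

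Model: reading = visit effect (SD s_v) + within-visit noise (SD s_w), both normal, with changes rounded to whole units.
- SD of change against Day 1 = √(2(s_v² + s_w²))
- SD of change against same-day pre-dose = √2 · s_w
- After rounding, a fall of at least 20 means a change of −19.5 or below. With no drug effect, the chance per reading is Φ(−19.5/SD). The chance for a session (either reading) was simulated, because the two readings share a reference.
- With a true 28 mmHg fall at one reading, the chance of a flag is Φ((28 − 19.5)/SD) = Φ(8.5/SD).

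| s_v, s_w (mmHg) | SD, Day 1 / same day | False flag per session, Day 1 / same day | True 28 mmHg fall flagged, Day 1 / same day |
|---|---|---|---|
| 6, 4 | 10.20 / 5.66 | 4.1% / 0.1% | 80% / 93% |
| 8, 5 | 13.34 / 7.07 | 10.1% / 0.6% | 74% / 89% |
| 10, 5 | 15.81 / 7.07 | 14.1% / 0.6% | 70% / 89% |

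For example, in the first row Φ(8.5/10.20) = Φ(0.83) = 0.80 and Φ(8.5/5.66) = Φ(1.50) = 0.93.

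The 12 new subjects have 12 × 2 = 24 later sessions. Expected spurious systolic-fall flags are 24 × 0.041 to 24 × 0.141, about 1.0 to 3.4, against Day 1. Against the same-day value they are 24 × 0.001 to 24 × 0.006, about 0.02 to 0.14.

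For a pulse change of at least 15 bpm in one direction (s_v, s_w = 5, 4; 7, 4; 8, 5), the false-flag rate per session is 8–19% versus 1–4%.

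**Sensitivity to the SDs.** With a second set (within/between 4/4, 5/7, 7/9 mmHg) and systolic changes in either direction, the false-flag rate per reading is 1.2%, 10.0% and 21.5% against Day 1, versus 0.04%, 0.5% and 4.3% same-day. The direction holds throughout; the size depends heavily on the SDs.

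**Adding the absolute limit.** Table 10 also flags systolic pressure at or below 90 mmHg, which needs no baseline. Including it for the true 28 mmHg fall, with the SDs in the table, the same-day advantage is about 6–11 percentage points at a mean systolic pressure of 110 and 11–15 at 115. At 120–125 the limit adds little. On the change criterion alone it is 13–19 points.

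**The case against.** The strongest reply is that little is lost. The pre-dose readings on Days 22 and 43 are themselves time points in SAP 7.7.4. With complete data, mean(post − Day 1) − mean(pre − Day 1) = mean(post − pre), so the average acute shift can be read from adjacent rows. Individual values are listed, and with about 19 dosed subjects the listing is short. If PCI counts are shown by time point, a visit-level shift would often be flagged before dosing too. The protocol's safety endpoint is change from baseline at each visit, which the SAP delivers. No hypothesis or stopping rule uses the flags.

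Most of that stands, and it limits the point. It does not repair the tables: the SD of the acute change and the individual flags cannot be recovered from the summaries, SAP 7.7.4 does not say that PCI counts are split by time point, and the listing leaves the subtraction to the reader.

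A reader might go further and infer that acute reactions would be missed at sessions II and III. The documents do not support this. Subjects stay under direct observation for 30 minutes and until they show no sign of a reaction (Protocol 6.3). The investigator reviews every vital sign for clinical significance (Protocol 8.2.5), hypersensitivity is an event of special interest (Protocol 8.3.7), and the absolute PCI limits need no baseline.

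**Conclusion.** The point holds for the planned vital-sign change and PCI tables on Days 22 and 43. The better reference is collected but not used, so flags there can be spurious and acute changes can be hidden. Under the assumed SDs, false systolic-fall flags are about 4–14% of sessions versus 0.1–0.6%. The loss of sensitivity is more modest, and smaller still where the 90 mmHg limit comes into play. All rates rest on a normal model and SDs that are not in the documents. This is a defect in descriptive safety summaries, worth correcting because the correction is nearly free.

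Two wider readings are not supported. A reader might conclude that no same-day reference exists; it does, and it is summarised and listed. A reader might also extend the point to local tolerability, because the schedule's complete-before-dosing note applies "with the exception of injection site reactions/local tolerability in the areas treated". The SAP baseline definition does not govern those reactions. They are reported as adverse events of special interest with onset dates, subjects are asked at each visit about events since the last one (Protocol 8.3.2), and the area is photographed before it is marked on each dosing day. The exemption allows assessment after dosing; it does not forbid an earlier look.

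**What to change.** In SAP Table 12, add a session baseline: the last non-missing value before that day's injections. In SAP 7.7.4, summarise the 15- and 30-minute changes on Days 1, 22 and 43 against it, and state in 4.6.3 that the change part of the PCI criteria uses it for those readings. Keep the existing Day 1 baseline for pre-dose values on Days 22 and 43 and for non-dosing visits, so that longer-term drift remains visible. Leave the absolute limits as they are. State whether PCI counts are shown by time point.

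The cost is one derived variable and one extra set of columns, from data already collected. The SAP needs updating in any case, because its section 8 rests on the original protocol and Amendment 1, while the current protocol is Amendment 3. No change to local-tolerability recording is part of this fix.

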6.3. Handling of Missing Data

Subjects who discontinue the study any time after the initiation of the study drug will not be replaced and available data of these subjects until the point of discontinuation will be summarized. The missing baseline assessment will not be imputed.

For categorical variables with missing values, a category documenting the frequency of missing values will be displayed in the summary tables.

Subjects who discontinue early will be encouraged to complete all end of study (EOS) procedures and assessments at an early termination visit.

There will be no imputation of missing values for safety data, however missing relationship between AE and study drug will be considered as related to study drug following worst case principle. Missing severity of an AE will be summarized as a severe AE.

Immunogenicity samples with a positive titer value will undergo a log transformation for analyses. Samples with titer levels less than 1 will be assigned or imputed as a log transformed titer of 0 for analyses.

6.3.1. Imputation of Partial Dates

The following rules will apply in cases of partial dates in concomitant medications and procedures:

- If the start date is partial with month and year present, then missing day will be imputed with the first day of the month. Whereas if the end date is partial with month and year present then missing day will be imputed with the last day of the month.
- If only year is present in the start date, then missing day and month will be imputed with first day of January. Whereas if only year is present then missing day and month will be imputed with the last day of December.

6.3.1.1. Concomitant Status of Medication for Unknown Start Date

The following rules will apply in cases where the start date of a concomitant medication is completely unknown:

- If the medication onset date is unknown and the end date is on or after the Screening Visit date or medication is ongoing, then the medication will be considered as concomitant.
- If the medication onset date is unknown and the end date is before the Screening Visit date, then the medication will not be considered as concomitant.
- If both the start and end dates are unknown, then the medication will be considered as concomitant. This approach is considered to be the most conservative following the worst-case principle.
- If the medication onset date is partly present and month/year is before informed consent date, then the medication will not be considered as concomitant.

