4.3. Prior/Concomitant Medications and Procedures

All medications will be coded using the World Health Organization (WHO) Drug Dictionary by active ingredient and anatomical therapeutic chemical (ATC) classification of ingredients. The dictionary version used is defined in the Data Management Plan.

Any medications/procedures within 90 days prior to the Screening Visit will be classified as prior medications/procedures.

Any medications/procedures from the Screening Visit through the Day 265 Visit will be classified as concomitant medications/procedures.

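### SAP 6.3.1.1 classifies a medication with a partial pre-consent start date as not concomitant even when it is ongoing, contrary to SAP 4.3 and Protocol 6.7

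*SAP*

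**What the plan says.** SAP 4.3 sets the definition: "Any medications/procedures from the Screening Visit through the Day 265 Visit will be classified as concomitant medications/procedures". Protocol 6.7 likewise defines concomitant by when the product was taken. Neither uses the start date as the test. SAP 4.3 separately calls anything used in the 90 days before Screening prior.

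SAP 6.3.1 deals with partial dates by imputation: "If the start date is partial with month and year present, then missing day will be imputed with the first day of the month". A year-only start becomes 1 January. Partial end dates go to the last day of the month, or of the year.

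SAP 6.3.1.1 then lists status rules for cases "where the start date of a concomitant medication is completely unknown". There are four bullets:

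- Bullet 1: with an unknown onset, if "the end date is on or after the Screening Visit date or medication is ongoing, then the medication will be considered as concomitant".
- Bullet 2: with an unknown onset and a stop date earlier than Screening, the drug is classed as not concomitant.
- Bullet 3: with both dates unknown, the medication is concomitant, and the reason given is "This approach is considered to be the most conservative following the worst-case principle".
- Bullet 4: "If the medication onset date is partly present and month/year is before informed consent date, then the medication will not be considered as concomitant".

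SAP 7.5 summarizes prior and concomitant medications on the Safety Population and lists them for all subjects.

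**The concern.** Bullets 1 and 2 decide status by whether use reached Screening, and bullet 3 resolves doubt in favour of counting the drug. Bullet 4 looks only at when the drug was started. It therefore answers a different question from the one SAP 4.3 asks, and it gives the less inclusive answer to the subject about whom more is known.

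The medications exposed to this are those begun before the study and continued through it. Inclusion criterion 8 lists hormonal methods among the acceptable forms of contraception. Contraceptive use must run from at least one menstrual cycle before the first dose through Day 251, while screening lasts at most 35 days, so such use can readily predate consent and continue past it. Aspirin up to 150 mg per day is permitted under Protocol 6.7.1. Bruising is an adverse event of special interest (Protocol 8.3.7), so the concomitant summary is one place a reader would look for that background. Either drug, recorded with a partial start date, would lose its concomitant status under bullet 4.

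**Working it through.** The plan gives no figure to reproduce and no arithmetic applies. The check applies each rule to the same medication, begun before consent, varying only how completely its start date is recorded and when it stopped.

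Inputs: SAP 4.3, SAP 6.3.1, the four bullets of SAP 6.3.1.1, and Protocol 6.7.

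| Use of the drug | Complete start date (SAP 4.3) | Wholly unknown start (bullets 1–3) | Partial start before consent (bullet 4 as written) | Partial start, imputed by 6.3.1, then SAP 4.3 |
|---|---|---|---|---|
| Ended before Screening | Not concomitant | Not concomitant | Not concomitant | Not concomitant |
| Ended on or after Screening | Concomitant | Concomitant | **Not concomitant** | Concomitant |
| Ongoing | Concomitant | Concomitant | **Not concomitant** | Concomitant |
| End date wholly unknown | Not settled | Concomitant | **Not concomitant** | Not settled |

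Reading across the rows:

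1. If the drug stopped before Screening, every route agrees and bullet 4 does no harm.
2. If use reached or passed Screening, bullet 4 alone disagrees with the definition. For example, an ongoing drug with a start recorded as March 2015 (an illustrative date) is imputed to 1 March 2015 and is concomitant under SAP 4.3. It is also concomitant under bullet 1 if the start is left wholly blank. Only bullet 4 removes it.
3. If the end date is wholly unknown, bullet 4 goes against the worst-case reasoning given for bullet 3.
4. The error runs one way. Bullet 4 can take drugs out of the concomitant category but never adds any, so concomitant use can only be under-counted.

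Two drafting points follow. Bullet 4 concerns partial dates, so it lies outside a list whose lead-in covers only wholly unknown ones. And because SAP 6.3.1 already imputes partial dates, the SAP offers two routes for the same record with different results in rows two and three. It is also unclear whether bullet 4 is meant to cover year-only dates, since it speaks of month and year.

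**The case against.** The strongest defence is that bullet 4 sits outside its own lead-in, so a careful programmer would set it aside, impute under SAP 6.3.1 and apply SAP 4.3, and nothing would be misclassified. One might also suppose the author meant only drugs that had stopped before Screening. Neither is safe. Bullet 2 states the stopped-before-Screening condition and bullet 4 does not, and a programmer who follows the bullet as written will misclassify. The two-route conflict is a reason to correct the text.

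Other objections do stand, and they limit what can be claimed:

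- A reader might infer that long-term medication in general drops out of the concomitant table. It does not. Only drugs with a partial start date before consent are affected.
- A reader might infer that affected drugs vanish. SAP 7.5 keeps them in the subject listing, and a drug in use right up to Screening also meets the 90-day definition of prior. Whether prior and concomitant use appear in separate tables depends on SAP Module 2, which is not among the documents reviewed.
- A reader might infer that prohibited anticoagulants or antiplatelets would go unnoticed. The documents do not rely on this summary to find them. Exclusion 6 bars subjects who need them or had them within 7 days before injection (low-dose aspirin excepted). Protocol 6.7.1 requires the Medical Monitor to be told immediately. SAP 4.2 names prohibited medication as a deviation type, and SAP 7.2 lists all deviations.
- A reader might want a percentage of the 12 newly dosed subjects. Neither document says how many start dates are partial, and the summary uses the Safety Population, so no percentage is supported.

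**Conclusion.** Bullet 4 of SAP 6.3.1.1 is wrong as written. It contradicts the concomitant definition in SAP 4.3 and Protocol 6.7, is inconsistent with bullets 1 to 3, and falls outside the scope of its own list. Followed literally, it under-counts concomitant use for exactly those medications that have a partial start date before consent and whose use continued to or past Screening, or whose end date is unknown.

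The number affected cannot be computed from the documents and could be zero. The consequence is confined to a descriptive medication summary in a small open-label study; no efficacy or safety endpoint depends on it. This is a minor correction. The conclusion assumes that the bullet is programmed as worded and that Module 2 contains no overriding instruction.

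**What to change.** Make two changes in SAP 6.3.1.1:

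1. Extend the lead-in so that it covers start dates that are *completely unknown or partial*. Without this, a corrected bullet would still lie outside the list.
2. Replace bullet 4 with: *If the onset date is partial and before informed consent, the medication is not concomitant only if its end date (after imputation per Section 6.3.1) is before the Screening Visit; if it ends on or after Screening, is ongoing, or the end date is unknown, it is concomitant.*

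With these changes the partial-date route agrees with SAP 4.3 wherever that definition gives an answer, and with bullet 3 where the end date is missing.

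The alternative is to delete bullet 4 and apply SAP 4.3 after the SAP 6.3.1 imputation. That is shorter, but it leaves a partial start with a wholly unknown end date unsettled, so the replacement is the more complete choice.

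The cost is about one sentence plus the lead-in, with no new data collection. SAP Section 8 bases the plan on the protocol up to Amendment 1, while the protocol now stands at Amendment 3, so the correction can go into a revision that is needed anyway.
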